#### 5.9.3.2 Hyperuricemia

*If Uric acid  $\geq 8.0$  mg/dL (476  $\mu$ mol/L)*

- Consider rasburicase (dose based on institutional guidelines).

- If rasburicase is used, sodium bicarbonate should not be used as this may exacerbate calcium phosphate precipitation.
- Recheck potassium, phosphorus, uric acid, calcium and creatinine.

*If Uric acid  $\geq 10$  mg/dL (595  $\mu$ mol/L)*

**OR**

*Uric acid  $\geq 8.0$  mg/dL(476  $\mu$ mol/L) with 25% increase and creatinine increase  $\geq 0.3$  mg/dL ( $\geq 0.027$  mmol/L) from pre dose level*

- Administer rasburicase (dose based on local guidelines and/or institutional standards).
  - When rasburicase is used, sodium bicarbonate should not be used as this may exacerbate calcium phosphate precipitation.
- Notify nephrology (or other acute dialysis service).
- Recheck potassium, phosphorus, uric acid, calcium and creatinine in 1 hour.
- If uric acid  $< 8.0$  mg/dL 1 hour later, repeat potassium, phosphorus, uric acid, calcium and creatinine 2 and 4 hours later, if no other evidence of tumor lysis.

#### 5.9.3.3 Hypocalcemia

*If Calcium  $\leq 7.0$  mg/dL (1.75 mmol/L) AND Patient symptomatic (e.g. muscle cramps, hypotension, tetany, cardiac arrhythmias)*

- Administer calcium gluconate 50 to 100 mg/kg IV slowly with EKG monitoring.
- Telemetry.
- Recheck potassium, phosphorus, uric acid, calcium and creatinine in 1 hour.
- If calcium normalized 1 hour later, repeat potassium, phosphorus, uric acid, calcium and creatinine 2 and 4 hours later, if no other evidence of tumor lysis.
- Calculate corrected calcium and check ionized calcium if albumin low.

#### 5.9.3.4 Hyperphosphatemia

*If Phosphorus increase of  $>0.5$  mg/dL AND  $>4.5$  mg/dL*

- Administer phosphate binder and recheck potassium, phosphorus, uric acid, calcium and creatinine.

*If Phosphorus  $\geq 5.0$  mg/dL (1.615 mmol/L) with  $\geq 0.5$  mg/dL (0.16 mmol/L) increase*

- Administer a phosphate binder (eg, aluminum hydroxide, calcium carbonate, sevelamer hydroxide, or lanthanum carbonate).
- Nephrology (or other acute dialysis service) notification (dialysis required for phosphorus  $\geq 10$  mg/dL).
- Recheck potassium, phosphorus, uric acid, calcium and creatinine in 1 hour.
- If phosphorus  $< 5.0$  mg/dL 1 hour later, repeat potassium, phosphorus, uric acid, calcium and creatinine 2 and 4 hours later, if no other evidence of tumor lysis.

#### 5.9.3.5 Creatinine

*Increase  $\geq 25\%$  from baseline*

- Start or increase rate of IV fluids.
- Recheck potassium, phosphorus, uric acid, calcium and creatinine.

## 6.0 ANTICIPATED TOXICITIES & DOSE MODIFICATION/ DELAY GUIDELINES

### 6.1 Anticipated Toxicities

#### 6.1.1 Venetoclax

Per the IB version 11 dated Jun 2019 the expected toxicities for venetoclax are as follows:

System Organ Class	Adverse Reactions
Blood and lymphatic (including hematological labs)	
Very Common	Anemia, neutropenia, febrile neutropenia, thrombocytopenia
Common	lymphopenia
Gastrointestinal	
Very Common	Constipation, diarrhea, nausea, vomiting, abdominal pain, mucositis
General disorders and administration site conditions	
Very Common	Fatigue, edema
Infections and infestations	
Very Common	Pneumonia, upper respiratory tract infection
Common	Sepsis, urinary tract infection
Investigations	
Common	Blood creatinine increased, blood phosphorus increased, lymphocyte count decreased, neutrophil count decreased, serum albumin decreased
Uncommon	Blood calcium decreased, blood potassium increased, hemoglobin decreased
Metabolism and Nutrition Disorders	
Common	Hyperkalemia, hyperphosphatemia, hyperuricemia, hypocalcemia, hyponatremia, tumor lysis syndrome
Musculoskeletal and connective tissue disorders	
Very Common	Musculoskeletal pain, arthralgia
Nervous system disorders	
Common	Headache, dizziness
Respiratory, thoracic and mediastinal disorders	
Common	Dyspnea, cough
Skin and subcutaneous tissue disorders	
Very Common	rash
Vascular disorders	
Common	Hypertension
Very common ( $\geq 1/10$ ); Common ( $\geq 1/100$ to $< 1/10$ ); Uncommon ( $\geq 1/1,000$ to $< 1/100$ ); Rare ( $\geq 1/10,000$ to $< 1/1,000$ ); Very rare ( $< 1/10,000$ ); not known (cannot be estimated from the available data).	

#### 6.1.2 Romidepsin

Per the package insert dated March 2020 the expected toxicities for romidepsin are as follows:

System Organ Class	Adverse Reactions
Blood and lymphatic (including hematological labs)	
Very Common	thrombocytopenia, neutropenia, anemia, leukopenia
Common	febrile neutropenia
Gastrointestinal	

System Organ Class	Adverse Reactions
Very Common	nausea, vomiting, diarrhea, constipation, abdominal pain, stomatitis
General disorders and administration site conditions	
Very Common	Fatigue, edema, pyrexia, chills, peripheral edema
Infections and infestations	
Very Common	infections
Common	pneumonia, sepsis, cellulitis, HBV reactivation
Investigations	
Very Common	weight decreased, aspartate aminotransferase increased, alanine aminotransferase increased
Common	ECG T-wave changes, blood bilirubin increased
Metabolism and Nutrition Disorders	
Very Common	anorexia, hypokalemia
Common	dehydration, hypocalcemia, tumor lysis syndrome
Musculoskeletal and connective tissue disorders	
Very Common	Musculoskeletal pain, arthralgia
Nervous system disorders	
Very Common	disguesia, headache
Respiratory, thoracic and mediastinal disorders	
Very Common	dyspnea, cough
Common	hypoxia
Cardiac disorders	
Very Common	tachycardia
Common	ventricular arrhythmia
Vascular Disorders	
Very Common	hypotension
Common	deep vein thrombosis
Very common ( $\geq 1/10$ ); Common ( $\geq 1/100$ to $< 1/10$ ); Uncommon ( $\geq 1/1,000$ to $< 1/100$ ); Rare ( $\geq 1/10,000$ to $< 1/1,000$ ); Very rare ( $< 1/10,000$ ); not known (cannot be estimated from the available data).	

## 7.0 DOSE DELAY/ MODIFICATION GUIDELINES

---

### 7.1 General Information

- Baseline values are from screening evaluations.
- For supportive care guidelines see [Section 5.9](#).
- Venetoclax doses missed for toxicity will not be made up.
- Romidepsin doses missed for toxicity will not be made up.
- Permanently **discontinue protocol therapy** if:
  - Participant requires a dose reduction and is already on 100 mg/day of venetoclax
  - Participant requires a dose reduction and is already on 10 mg/m^2 romidepsin
  - Unable to resume treatment within 14 days after last dose of venetoclax
- If the venetoclax dose was reduced during Cycle 1, intra-patient daily re-escalation to steady-state venetoclax dose may be permitted in the absence of a recurrence of the toxicity that led to the reduction following consultation with the Study PI.
- The initiation of a new cycle may be delayed for up to 7 days with written approval from the Study PI in circumstances where the participant is unable to come to the clinic as planned to initiate the new cycle (e.g. planned vacation by participant, lack of transportation etc.).\*

\*If prior approval from the Study PI is obtained, then these modifications will not be considered a protocol deviation. The Study PI will document assessment of the impact of these determinations on the study design, objectives and endpoints or risk to participants. If any modifications to the treatment plan might affect the study design, objectives, and endpoints, or impact the risk of participants, a single subject exception will be sought by the IRB. If the treating investigator is the Study PI, the determination and the rationale for the determination will clearly be documented in the source document(s).

### 7.2 Treatment Modification Guidelines

Toxicity	Treatment Modification	
Metabolic and nutrition	Romidepsin	Venetoclax
Hyperuricemia, hyperphosphatemia, hyperkalemia, hypocalcemia and creatinine changes with no evidence of clinical TLS (See Appendix B ).  Potassium > 6.0 mmol/L  Potassium ≥ 0.5 mmol/L increase from prior value (even if potassium within normal limits [WNL])  Potassium > upper limit of normal Phosphorus > 4.5 mg/dL (1.5 mmol/L)  Uric acid > 8.0 mg/dL (475.8 µmol/L)		
 
• Hold the dose until resolution
 
• Refer to Section 5.10.3 for recommended supportive care.
 
• 1st occurrence 
 
– If resolved within 3 days to resume at the same dose
 
– If toxicity resolves > 3 days resume at a 50% dose reduction
 
 
 
• 2nd occurrence 
 
– If resolves within 3 days to ≤ Grade 1 or baseline,
 
 
 

Toxicity	Treatment Modification	
Metabolic and nutrition	Romidepsin	Venetoclax

Corrected calcium <7.0 mg/dL
 
Creatinine increase ≥ 25% from baseline
		
resume at a 50% dose reduction
 
 
– If toxicity lasts > 3 days permanently discontinue protocol therapy
 

Symptoms suggestive of clinical TLS (e.g. acute renal failure, cardiac arrhythmia, seizures) See Appendix B.
		
 
• Hold venetoclax dose until TLS is resolved
 
• If toxicity resolves within 24-48 hours resume venetoclax at current dose
 
• If toxicity takes longer than 48 hours to resolve, resume at the previous dose in the ramp sequence.2nd occurrence, consider permanently discontinuing protocol therapy
 


Other Grade 4 metabolic laboratory abnormalities
		
 
• Hold the dose until resolution to ≤ Grade 2 or baseline
 
• 1st occurrence 
 
– If resolved within 3 days to resume at the same dose
 
 
 
• If toxicity resolves > 3 days resume at a 50% dose reduction
 
• 2nd occurrence 
 
– If resolves within 3 days to ≤ Grade 2 or baseline, resume at a 50% dose reduction
 
– If toxicity lasts > 3 days permanently discontinue protocol therapy
 
 
 

Hematologic	Romidepsin	Venetoclax

Grade 3 neutropenia <1000 - 500/mm^3
	
 
• 1st occurrence 
 
– Hold until ANC ≥1.5 x 10^9/L
 
– Restart at prior dose
 
 
 
• 2nd occurrence 
 
– Hold until ANC ≥1.5 x 10^9/L
 
– Dose reduce to 12 mg/m^2
 
 
 
	
 
• Hold the dose until ANC ≤ Grade 2 or baseline
 
• Consider using G-CSF
 
• Resume at pre-hold dose
 

Toxicity	Treatment Modification	
Metabolic and nutrition	Romidepsin	Venetoclax
	
 
• 3rd occurrence
 
• Remove from trial
 
	
Grade 4 neutropenia $<500/\text{mm}^3$	
 
• 1st occurrence 
 
– Hold until ANC <math>\geq 1.5 \times 10^9/\text{L}</math>
 
– Restart at prior dose
 
 
 
• 2nd occurrence 
 
– Hold until ANC <math>\geq 1.5 \times 10^9/\text{L}</math>
 
– Dose reduce to <math>12 \text{ mg/m}^2</math>
 
 
 
• 3rd occurrence 
 
– Remove from trial
 
 
 
	
 
• Hold the dose until ANC <math>\leq</math> Grade 2 or baseline
 
• Consider using G-CSF
 
• Consider a 50% dose reduction per investigator discretion
 

Grade 3 febrile neutropena  G3: <math>< \text{ANC} < 1000/\text{mm}^3</math> with a single temperature of <math>> 38.3 \text{ degrees C}</math> (101 degrees F) or a sustained temperature of <math>\geq 38 \text{ degrees C}</math> (100.4 degrees F) for more than one hour.		
 
• Hold the dose until ANC <math>\leq</math> Grade 2 or baseline
 
• Consider using G-CSF
 
• Consider a 50% dose reduction per investigator discretion
 

Grade 4 febrile neutropena  G4: life threatening consequences	
 
• 1st occurrence 
 
– Hold until cytopenia returns to Grade 1 or baseline
 
– Restart at prior dose
 
 
 
• 2nd occurrence 
 
– Hold until ANC <math>\geq 1.5 \times 10^9/\text{L}</math>
 
– Dose reduce to <math>12 \text{ mg/m}^2</math>
 
 
 
• 3rd occurrence 
 
– Remove from trial
 
 
 
	
 
• Hold the dose until ANC <math>\leq</math> Grade 2 or baseline
 
• Consider using G-CSF
 
• Consider a 50% dose reduction per investigator discretion
 

Grade 3-4 thrombocytopenia, and/or anemia, and/or thrombocytopenia requiring transfusion	
 
• 1st occurrence 
 
– Hold until platelet count <math>\geq 75 \times 10^9/\text{L}</math> or baseline
 
– Restart at prior dose
 
 
 
• 2nd occurrence 
 
– Hold until platelet count <math>\geq 75 \times 10^9/\text{L}</math> or baseline
 
– Dose reduce to <math>12 \text{ mg/m}^2</math>
 
 
 
• 3rd occurrence 
 
– Remove from trial
 
 
 
	
 
• Grade 4 other unspecified hematologic toxicities (except lymphopenia)
 
• For Grade 4 thrombocytopenia 
 
– Hold the dose until platelets <math>\leq</math> Grade 2 or baseline
 
 
 
• 1st occurrence, 
 
– resume at same dose if toxicity resolves within 7 days
 
 
 
• consider a 50% dose reduction if toxicity lasts <math>> 7</math> days 2nd
 

Toxicity	Treatment Modification	
Metabolic and nutrition	Romidepsin	Venetoclax  occurrence and subsequent occurrence, – consider a 50% dose reduction if toxicity resolves within 7 days if toxicity lasts > 7 days, consider permanently discontinuing protocol therapy
Other unspecified Non-hematologic- RELATED	Romidepsin	Venetoclax
$\geq$ Grade 3	
 
• 1st occurrence 
 
– Hold until resolved to <math>\leq</math> Grade 1
 
– then reduce to 12 mg/m^2
 
 
 
• 2nd or 3rd occurrence Grade 3 
 
– Hold until resolved to <math>\leq</math> Grade 1
 
– Dose reduce to 10 mg/m^2
 
 
 
• Any recurrence of Grade 4
 
• Remove from trial therapy
 
	
 
• Hold the dose until <math>\leq</math> Grade 1 or baseline
 
• 1st occurrence, 
 
– resume at same dose if toxicity resolves within 7 days
 
 
 
• consider a 50% dose reduction if toxicity lasts > 7 days 2nd occurrence and subsequent occurrence,
 
– consider a 50% dose reduction if toxicity resolves within 7 days
 
– if toxicity lasts > 7 days, consider permanently discontinuing protocol therapy
 

Other unspecified Non-hematologic- UNRELATED	Romidepsin	Venetoclax
Any Grade	
 
• 1st occurrence 
 
– Maintain protocol therapy for Grades 0-2
 
– Hold until resolved from Grade 3-4 to <math>\leq</math> Grade 1
 
– Dose reduce to 12 mg/m^2
 
 
 
• 2nd or 3rd occurrence Grade 3 
 
– Hold until resolved to <math>\leq</math> Grade 1
 
– Dose reduce to 10 mg/m^2
 
 
 
• Any recurrence of Grade 4 
 
– Remove from trial therapy
 
 
 
	
 
• Maintain protocol therapy
 
• Interruption of protocol therapy is permitted if the investigator consults the Study PI to determine that this is in the best interest of the participant.
 

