### 2.3.2 Clinical experience

As of version 11 of the venetoclax Investigator's Brochure [29] a total of 2939 subjects received at least 1 dose of venetoclax in AbbVie studies and had data available as of 28 November 2018. Among these 2939 subjects, 1313 subjects had CLL/small lymphocytic leukemia (SLL), 570 subjects had non-Hodgkin's lymphoma (NHL), 218 subjects had multiple myeloma (MM), 361 had acute myeloid leukemia (AML), 59 subjects had myelodysplastic syndrome (MDS), 20 subjects had acute lymphocytic leukemia (ALL) and 219 were healthy volunteers. A total of 1137 received the drug as monotherapy, and 1406 received the drug in combination with other therapies. Doses administered in venetoclax clinical studies have ranged from 20 mg to 1200 mg.

The most common adverse events (incidence > 20%) reported for all subjects in monotherapy studies were nausea, diarrhea, neutropenia, anemia, thrombocytopenia and lymphopenia. Infections, including serious infections, although also common with the underlying malignancies, have been reported with venetoclax treatment and their incidence is higher with combination treatments. The most common adverse events that were grade 3 and above were neutropenia (31.0%) and anemia (13.8%). The most common serious adverse events were febrile neutropenia and malignant neoplasm progression (5.7% each). The most common treatment emergent adverse event that led to death was malignant neoplasm progression (2.1%).

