#### *Hematologic*

- Grade 3 or 4 neutropenia lasting > 7 days (despite the use of growth factor support)
- Grade 3 or 4 thrombocytopenia associated with bleeding requiring transfusion
- Grade 4 anemia not associated with lymphoma

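### Section 7.2 releases the romidepsin hold for Grade 3-4 anemia on a platelet count, so for isolated anemia with adequate platelets the hold has no effect

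*Combined protocol and SAP*

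**What the plan says.** The Section 7.2 table has separate columns for romidepsin and venetoclax. One hematologic row has the trigger "Grade 3-4 thrombocytopenia, and/or anemia, and/or thrombocytopenia requiring transfusion". Its romidepsin column runs as follows.

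- First occurrence: "Hold until platelet count" is at least 75 x 10^9/L or baseline, then restart at the prior dose.
- Second occurrence: same release, then 12 mg/m2.
- Third occurrence: removal.

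The venetoclax cell of the same row also states a release value for platelets only (Grade 2 or lower, or baseline, after Grade 4 thrombocytopenia). Its later steps turn on how quickly the toxicity resolves.

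Other romidepsin cells tie release to the abnormality that caused the hold. The Grade 3 and Grade 4 neutropenia rows say "Hold until ANC" is at least 1.5 x 10^9/L. The Grade 4 febrile neutropenia row, at first occurrence, says "Hold until cytopenia returns to Grade 1 or baseline".

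In the clinical-TLS row the instruction is "Hold venetoclax dose until TLS is resolved", followed by rules for resuming venetoclax. Nothing is stated for romidepsin at a first event.

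**The concern.** A dose hold is meant to let the toxicity recover before the next dose. Here the recovery test for anemia is made on a different blood count. If platelets are adequate, the test is passed before any recovery has begun, and romidepsin may continue through severe anemia. The episode is nevertheless recorded as an occurrence, so the rule can lower the dose and end treatment without ever having given a pause. This is a patient-safety matter in the text that sites use for dosing.

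The clinical-TLS row raises a smaller question of the same kind. The protocol links TLS to romidepsin as well as venetoclax (Sections 2.7, 5.5 and 6.1.2). The Day 8 infusion falls within the Day 1-8 TLS monitoring period, yet the row instructs on one drug only.

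**Working it through.** The plan gives no figure to reproduce. The check is a reading of the table and of the sections that might supply the missing rule, plus short arithmetic on size and cost.

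**1. Does isolated anemia trigger the row?** Yes. The conditions are joined by and/or, so anemia alone is enough.

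**2. Does the release refer to anemia?** No. The words on baseline follow the platelet count and read as baseline platelets. Section 3.1 admits patients with platelets from 30,000/mm3 (30 x 10^9/L), so this alternative can be met well below 75.

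**3. Applying the rule:**

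| Patient | Release test at onset | Result |
|---|---|---|
| Grade 3-4 anemia, platelets 75 x 10^9/L or more | Met | Hold of 0 days |
| Grade 3-4 anemia, platelets below 75 but at baseline | Met | Hold of 0 days |
| Grade 3-4 anemia and low platelets | Not met | Held until platelets recover, whatever the anemia |
| Thrombocytopenia only | Not met | Works as intended |

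In all four rows the second episode reduces the dose by (14 - 12)/14 = 14.3% and the third ends treatment.

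**4. Does another section supply an anemia release for romidepsin?**

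- Section 7.1 gives general rules and no hemoglobin or anemia-grade criterion.
- The Section 10.0 calendar schedules blood counts, which detect anemia.
- Section 5.9 covers supportive care, which treats it.
- Section 11.2 lists "Grade 4 anemia not associated with lymphoma" as an unacceptable toxicity, which counts it.
- Section 2.7 says romidepsin dosing follows the label. The label is not in the documents and no release rule from it is reproduced.

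None is a written release criterion.

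**5. How many patients?** The documents do not say. As an illustration only, Section 2.3.2 gives 13.8% for anemia of Grade 3 or above with venetoclax, in a passage on monotherapy studies. Applied to 18 patients, 18 x 0.138 = 2.5 would be expected to have such anemia. The share with adequate platelets is not given, so a range is assumed:

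| Share with adequate platelets | Expected patients | Chance of at least one |
|---|---|---|
| 25% | 18 x 0.0345 = 0.6 | 1 - (1 - 0.0345)^18 = 47% |
| 50% | 18 x 0.069 = 1.2 | 1 - (1 - 0.069)^18 = 72% |
| 100% | 18 x 0.138 = 2.5 | 1 - (1 - 0.138)^18 = 93% |

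**6. What would a working hold do to evaluability?** Section 12.3 requires at least 75% of the total dose of each drug over the first two cycles. Planned romidepsin is 6 infusions x 14 = 84 mg/m2.

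- One missed: 70/84 = 83.3%, still evaluable.
- Two missed: 56/84 = 66.7%, so a lead-in patient would be replaced unless an unacceptable toxicity had occurred.

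**7. Clinical TLS.** The row names venetoclax, so a lost or merged table cell does not explain the silence on romidepsin. Section 5.2 allows either drug to be held while a cycle starts, so a venetoclax hold does not imply a romidepsin hold. Section 12.4.1 suspends accrual and Section 14.5 requires notification; neither is a dosing rule for the affected patient.

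**The case against.** The strongest reply is that no sensible clinician would be misled. Section 5.6 lets the investigator stop treatment when the patient's condition warrants, Section 2.7 defers to the label, and severe anemia would be transfused and watched. The venetoclax cell of the row appears to contain a misplaced toxicity label, so the table layout may be damaged. The frequencies above come from a different drug regimen and other diseases, and the platelet shares have no source.

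Part of this stands. The frequencies are assumptions; the 93% needs every anemic patient to have adequate platelets. But layout damage does not rescue the anemia rule: the trigger names anemia and the release names platelets. Discretion may correct a wrong rule at the bedside, but it does not make the rule right.

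For TLS the reply is much stronger. A reader might infer that the plan directs a Day 8 infusion during unresolved TLS. The documents do not support that. The text with Table 5.9.1 leaves the management of diagnosed TLS to each institution while also pointing back to the dosing table. The label may speak to it. The rows for other unspecified non-hematologic toxicity, which hold romidepsin for Grade 3 or higher events and then reduce it, arguably apply because nothing is specified for romidepsin. What remains is a missing sentence.

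A reader might also infer the same gap for laboratory TLS. There the hold names no drug in the text as read. Some triggers are mild, such as a potassium "increase from prior value (even if potassium within normal limits [WNL"). Whether such changes should stop romidepsin is a clinical judgement.

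**Conclusion.** The anemia rule is wrong as written and should be corrected. For isolated Grade 3-4 anemia with platelets at or above 75 x 10^9/L, or at baseline, the effective romidepsin hold is 0 days. With both cytopenias, release ignores the anemia. Reduction at the second episode and removal at the third apply regardless. This conclusion rests on the wording alone and needs no assumption about frequency, which the documents do not give.

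The clinical-TLS point is a minor clarification: an instruction is absent that other provisions may already lead to in practice.

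Nothing here touches the Simon two-stage design, its type I error, its power or the 18 evaluable patients.

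**What to change.** In the Section 7.2 row:

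- Give anemia its own romidepsin release, for example hold until anemia is Grade 2 or lower, or baseline. State whether a post-transfusion hemoglobin counts; if it does, a transfusion could end the hold almost at once.
- Keep the platelet criterion for thrombocytopenia only. Where both are present, require both.
- State the matching anemia release in the venetoclax cell.

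In the clinical-TLS row, add one sentence that romidepsin is also held until clinical TLS resolves. Leave the laboratory-change row and the rows for other unspecified toxicity as they are.

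The cost is a table edit in an amendment, with no new tests. The downside is an occasional delayed romidepsin dose, or a missed one that Section 7.1 does not allow to be made up. A single missed infusion does not threaten lead-in evaluability; two within the first two cycles could.

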## 8.0 AGENT INFORMATION

### 8.1 Venetoclax

Venetoclax has been FDA approved for patients with chronic lymphocytic leukemia (CLL) with 17p deletion, as detected by an FDA approved test, who have received at least one prior therapy.

For additional information refer to the IB.

